Brief Summary	This RCT will test a new electronic health record module to improve guideline-compliant care of older adults with diabetes. The module incorporates effective behavioral economics (BE) principles to improve the degree to which care of older adults is compliant with Choosing Wisely (CW) guidelines; this generally involves less aggressive targets for HbA1c, and reductions of medications other than metformin. The implementation of the module is triggered by patient scheduling and medication prescribing in EPIC. The BE principles include suggesting alternatives to medications, requiring justification, setting of appropriate default order sets, and incorporation of anchoring and checklists to guide behavior.
Objectives	Primary objective: to test a customized EHR toolkit that applies BE insights to promote appropriate diabetes care in older adults based on the American Geriatric Society's Choosing Wisely guideline, and to assess the acceptability of the resulting module. Secondary objective: to assess the "usability" of the proposed BE-EHR module in clinical practice.
Methodology	Cluster-randomized controlled trial
Endpoints	Primary endpoint: Choosing Wisely guideline compliance Secondary endpoint: medication prescribing patterns
Study Duration	Eighteen months
Participant Duration	Eighteen months
Population	Patients age 75 or older with diabetes
Study Sites	One single site at NYULH consisting of approximately 70 outpatient practices in primary care, geriatrics, or endocrinology
Number of participants	Approximately 5000
Statistical Analysis	We will begin all analyses with descriptive summary statistics and graphical displays of all variables. Primary analyses will utilize Poisson mixed-effects models for the provider-level CW compliance rate, with treatment group as the primary fixed effect of interest and practice as a random effect to accommodate clustering of providers within practices. We will assess whether negative binomial regression is warranted because of overdispersion. We will also explore non-parametric methods such as quantile regression and other rank-based approaches. Although randomization should obviate the need for any additional adjustment, we will explore whether adjustment for provider-level characteristics, such as demographics, panel size, or insurance mix, is necessary.

Schematic of Study Design

Prior to Enrollment	Identify ~70 NYULH clinics to participate
	\int
Randomization	Randomize evenly in a 1:1 ratio to receive the standard EPIC instantiation or the standard EPIC instantiation plus the BE-EHR module.
	Ţ
Evaluation	Evaluate Choosing Wisely compliance rate in patients meeting eligibility seen at participating practices

1 Key Roles

PI: [name], Professor of Population Health and Director of Biostatistics NYU School of Medicine [name] [contact] [contact]

Sub-I: [name], Associate Professor of Medicine and Population Health NYU School of Medicine [name] [contact] [contact]

Sub-I: [name], Assistant Professor of Medicine and Population Health NYU School of Medicine [name] [contact] [contact]

Sub-I: [name], Assistant Professor of Population Health NYU School of Medicine [name] [contact] [contact]

Sub-I: [name], Postdoctoral Fellow NYU Langone Health [name] [contact] [contact]

2 Introduction, Background Information and Scientific Rationale

2.1 Background Information and Relevant Literature

2.1.1 Intensive glycemic control is of unclear benefit and carries increased risk for older adults with diabetes. A number of randomized controlled trials, including the Action to Control Cardiovascular Risk in Diabetes (ACCORD) trial,¹ the Action in Diabetes and Vascular Disease: Preterax and Diamicron Modified Release Controlled Evaluation (ADVANCE) trial,² and the Veterans Affairs Diabetes Trial (VADT)³, found that intensive glycemic control was not protective for macrovascular complications of diabetes including myocardial infarction or stroke. Although the United Kingdom Prospective Diabetes Study (UKPDS) did find a reduction in myocardial infarction in the long term after intensive glycemic control, this study enrolled middle-aged patients at time of diabetes diagnosis.⁴ ACCORD,⁵ ADVANCE,² and UKPDS⁶ all suggested improvements in microvascular complications with tight glycemic control, but these often take years to develop. In total, these trials suggest that tight glycemic control is primarily beneficial to patients with newly diagnosed diabetes and a long life expectancy; these characteristics do not apply to most older patients, many of whom have been living with diabetes as a chronic disease.⁷ Furthermore, these trials demonstrated the potential for harm with tight glycemic control, notably

CONFIDENTIAL

increased risk of hypoglycemia,^{1,2} as well as a suggestion of increased all-cause mortality.¹ Indeed, older adults are particularly susceptible to harms related to hypoglycemia in diabetes, including emergent hospitalization and neurologic complications.⁸⁻¹² Intensive glycemic treatment may also lead to increased risk of polypharmacy and adverse medicine interactions for older adults with multiple chronic conditions.¹³

2.1.2 The American Geriatric Society's Choosing Wisely guideline recommends moderate glycemic control. The third Choosing Wisely recommendation from the American Geriatric Society is: "Avoid using medications other than metformin to achieve hemoglobin A1c<7.5% in most older adults; moderate control is generally better."¹⁴ Furthermore, as shorter life expectancy and greater comorbidity burden may decrease the benefits and increase the risks of tight glycemic control, the Choosing Wisely campaign suggests using these markers of health status to identify glycemic targets for older patients with diabetes. Glycemic target HbA1c ranges are provided for older adults in three categories: 7.0-7.5% for healthy adults with a long life expectancy. 7.5-8.0% for patients with moderate comorbidity and a life expectancy. of less than 10 years, and 8.0-9.0% for patients with multiple comorbid conditions and a shorter life expectancy.^{7,15} These recommendations build on work by Co-investigator [name] on categorization of older adults with diabetes into three clinical groups based on health status;¹⁶ this has been endorsed by numerous expert panels and guidelines.^{11,17,18} The target ranges for glycemic control are similar to HbA1c values that have been associated with the best outcomes for older adults with comorbid conditions in observational or modeling studies.¹⁹⁻²¹ Additionally, the American Diabetes Association (ADA) and others have recommended similar health status categories related to HbA1c targets in older adults.^{11,17,18} Although the ADA guidelines do not identify lower targets for HbA1c,¹¹ other societies including the American Geriatric Society recommend similar lower thresholds for glycemic control.^{18,22-24} Unfortunately, despite these recommendations, a substantial number of older adults have intensive glycemic control that may not be necessary.²⁵⁻²⁷ Additionally, older patients with intensive alvcemic control generally do not undergo de-intensification of therapy, suggesting opportunity for improving appropriate care.28

2.1.3 Behavioral economic approaches offer promise in influencing hard-to-change behavior. The field of behavioral economics (BE) seeks to combine principles of standard economics and psychology to recognize the limitations of the classical economic framework that views human decision-makers as purely rational actors who make decisions by maximizing the outcomes of available choice sets (sometimes termed Homo economicus).²⁹ In reality, humans are predictably irrational,³⁰ making common decision errors that are explicable through a set of psychological principles, and are therefore *predictable*. The field of behavioral economics posits that these decision errors, once recognized, can be harnessed to encourage desired behaviors rather than inhibit them.³¹

2.1.4 Decision errors fall into a typology of recognizable classes with known mechanisms. Traits contributing to decision errors include loss aversion, anchoring, overweighting of small probabilities, present bias, regret aversion, sensitivity to defaults, and the power of social comparisons.³² Once recognized, each of these decision errors can be harnessed and overcome, often in the form of gentle "nudges" that make a desired behavior more likely.³³⁻³⁶ Loss aversion occurs when a loss is more distressing than a gain of equivalent value;^{37,38} thus, presenting rewards using a loss rather than a gain frame can be an effective motivator. Anchoring occurs when the decision-maker compares potential outcomes to some specified or implied reference level;³⁹ responses can be heavily influenced by the first information presented, so adjustment of the scale and/or starting point of a choice set can influence the resulting decisions. Present bias, also called hyperbolic discounting,⁴⁰ occurs when outcomes occurring in the near future carry much more weight than those occurring further into the future.⁴¹ Human beings tend to overweigh small probabilities, one feature that contributes to the popularity of lotteries.^{42,43} Regret aversion can be a highly motivating force in determining future actions.⁴⁴⁻⁴⁶ Regret lotteries are a behavioral economic intervention simultaneously targeting probabilistic errors, present bias, and regret; in this approach, rewards are contingent on a desired behavior and participants are informed that they would have won if they had only completed it.^{47,48} Defaults are a powerful driver of decisions, carrying implications of superiority or endorsement and taking advantage of decisional inertia; examples exist in such diverse domains as participation in retirement plans⁴⁹ and organ donation⁵⁰ that demonstrate dramatic differences in participation as a result of the chosen default option. Social comparisons have

CONFIDENTIAL

been shown in a number of settings to be effective in influencing behavior,^{24,51} as people tend to be heavily motivated by their perception of how their performance compares to those around them;^{52,53} the phenomenon of social desirability bias is well documented.^{54,55}

2.1.5 Substantial evidence shows the benefits and limitations of clinical decision support on clinical care. Electronic health records (EHRs) now dominate the landscape, influencing nearly every clinical decision, workflow, and order placed by health care providers. While EHRs have been successful in standardizing documentation, facilitating data sharing, and improving safety, their impact on clinical decision making has been mixed. Clinical decision support (CDS) is the primary EHR tool for influencing clinical decision making and promoting adherence to clinical guidelines. CDS entails providing clinicians, patients, and other healthcare stakeholders with pertinent knowledge, templates, and/or person-specific information, intelligently filtered or presented at appropriate times, to enhance health and healthcare.⁵⁶ CDS is an effective tool for improving provider performance and patient outcomes;⁵⁷ a meta-analysis of 25 randomized controlled trials found strong evidence that CDS improves care (odds ratio 1.42, 95% confidence interval 1.27 to 1.58).⁵⁸ Moreover, best practices for optimizing CDS effectiveness have been identified.^{59,60} Successful CDS must deliver accurate information in the right clinical context at the point of care, and must be integrated into the relevant provider's workflow.⁶¹ CDS can take many forms; to date, alerts and reminders have been the dominant CDS tools.⁶² Large systematic reviews of CDS have demonstrated a moderate ability to reduce morbidity, utilization, and costs.^{63,64} These modest improvements, however, are undermined by the well-documented problems of alert fatigue and poor workflow integration, which together blunt the potential impact of EHRs and CDS to improve healthcare outcomes.⁶²

2.1.6 New studies indicate that combining behavioral economic and EHR clinical decision support tools offers promise for improving guideline adherence. Integrating behavioral economics and electronic health records using various CDS tools is a novel approach to improving adherence to guidelines that also seeks to minimize negative impacts on clinical workflow and cognitive load. For example, Meeker et al. integrated three BE concepts (suggested alternatives, accountable justification, and peer comparisons) into the EHR at 50 primary care practices to significantly (~5-7%) reduce inappropriate antibiotic prescribing for upper respiratory infections.⁵¹ New approaches like these are needed to complement the traditional alerts, reminders, and other CDS tools that disrupt clinical workflow, increase cognitive load, and stress the limited capacity of clinicians to rationally process and evaluate the diverse and competing demands on their attention.

2.1.7 Innovation. This study will evaluate an innovative tool, implementing behavioral economic principles within the electronic health record, to promote clinician adherence to the Choosing Wisely guideline for diabetes management in older adults. Specific areas of innovation include:

- Minimal impact on clinician workflow or cognitive workload. Unlike most new CDS systems, the
 proposed BE-EHR module will have limited negative impact on clinical workflow and cognitive load.
 BE tools inherently bypass the central processing route that requires clinicians to actively think about
 decision making.⁶⁶ Instead it leverages the peripheral route, which uses contextual cues and other
 influencing tools to nudge clinicians to choose actions consistent with stated guidelines.
- **Extending the power of BE by combining modalities using the EHR.** Several BE approaches have demonstrated efficacy. By combining multiple BE approaches and packaging them in a customizable EHR module, we will amplify the potential impact of BE on clinician guideline adherence when treating older people with diabetes.
- A flexible, scalable, modular intervention. The creation of the BE-EHR module serves as a highly scalable platform for embedding BE-based CDS into any EHR system. The proposed module will guide other EHR users through a menu of customizable options that can switch on (or off) various BE-derived CDS tools to replicate our intervention for improving clinician adherence to diabetes management guidelines in older adults. More importantly, this module can be easily applied to many other conditions in older adults and other populations where combining BE with EHR-based clinical decision support will be useful for improving guideline adherence.

CONFIDENTIAL

• A scalable, interoperable, standards-based solution. The BE-EHR tool will follow standardsbased development approaches, enabling widespread adoption across healthcare systems and diverse EHR platforms.

2.2 Rationale

This study aims to evaluate a new BE-EHR module to improve adherence to Choosing Wisely guidelines among older adults with diabetes.

2.3 Potential Risks & Benefits

2.3.1 Known Potential Risks

The risk is not greater than minimal risk (i.e., risk encountered in daily life or in the course of usual clinical practice). Individual case determinations of potential safety gaps will never be released to supervisors of any clinicians whose charts are being reviewed. None of the study investigators has any oversight capacity over any clinicians.

2.3.2 Known Potential Benefits

There may be benefit to individual participants in this pilot study if their care is improved to comport with guidelines. The research will contribute critically to our knowledge of how to integrate behavioral economic interventions into EHR-driven clinical workflows. In the past, our team has successfully identified the potential benefit of connecting interventions with clinical workflows, and will assess a novel BE-EHR module to enable improved, guideline-consistent care of older adults with diabetes.

3 Objectives and Purpose

3.1 Primary Objective

The primary objective of the study is to evaluate a customized EHR toolkit that applies behavioral economic insights to promote appropriate diabetes care in older adults based on the American Geriatric Society's Choosing Wisely (CW) guideline.

3.2 Secondary Objectives (if applicable)

The secondary objective of the study is to continue to assess the usability of the proposed BE-EHR module in clinical practice.

4 Study Design and Endpoints

4.1 Description of Study Design

NYU Langone Health has ambulatory care sites in the five boroughs of New York City (NYC) as well as in suburbs of New York and New Jersey. Sites include academic practices, many community-based practices and a Federally Qualified Health Center (FQHC); many are multispecialty. Physicians in these practices form the NYU Faculty Group Practice (FGP) consisting of 351 total practices, including 81 primary care and 21 endocrinology practices. The NYU Brooklyn Family Health Center (FHC) is the second largest FQHC in the nation and has 9 additional clinics. All have the NYU Epic EHR, connecting all ambulatory visits at FGP clinics and at the FQHC. We will identify approximately 70 practices and conduct a parallel-groups cluster-randomized comparison of standard EPIC to standard EPIC + the BE-EHR module.

4.2 Intervention

The BE-EHR module includes six components: 1) a tailored advisory for patients over 75 with diabetes, 2) medication refill protocol with information on Choosing Wisely guidelines, 3) pre-population of the medication preference list with metformin, 4) lab result protocol with information on Choosing Wisely

CONFIDENTIAL

guidelines, 5) peer comparisons regarding performance meeting guidelines, and 6) media campaign with information about Choosing Wisely guidelines. The set of nudges is referred to collectively as the BE-EHR module.

To tailor the intervention appropriately, we use a life expectancy algorithm to address different target patient populations with different CW guidelines. The life expectancy algorithm was built into the BE-EHR module to drive timing and content of module firings that incorporate both patient life expectancy (high, medium, low) and target glycemic index per the CW guideline. These categories are defined as follows:

1) healthy older adults with long life expectancy (>10 years): HbA1c target range of 7-7.5%;

2) those with moderate comorbidity and a moderate life expectancy (3-10 years): HbA1c target range of 7.5-8%;

3) those with multiple comorbidities and shorter life expectancy (\leq 3 years): HbA1c target range of 8-9%.

4.3 Randomization

There are currently 81 primary care practices in our FGP. Practice sites will be randomized using variable block sizes of 4 and 6 to ensure balance, with an even randomization ratio that will result in half of the sites randomized to the BE-EHR module activation (BE-EHR) and half randomized to usual care (UC). Randomization will be stratified by practice size (<= 100 patients vs > 100 patients over 75 with diabetes) to ensure balance. [name] will request that the randomization scheme be generated by one of her faculty or staff members in the Division of Biostatistics who is unaffiliated with the project, in order to maintain blinding of assignment by the study team.

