5.1 Inclusion Criteria

- Patient at NYULH primary care or endocrinology practice
- Practices that have patients aged 75 or older
- Practices that have a diagnosis of diabetes in the EHR chart

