10.3 Statistical Methods

We will begin all analyses with descriptive summary statistics and graphical displays of all variables. Primary analyses will utilize Poisson mixed-effects models for the provider-level CW compliance rate, with treatment group as the primary fixed effect of interest and practice as a random effect to accommodate clustering of providers within practices. We will assess whether negative binomial regression is warranted because of overdispersion. We will also explore non-parametric methods such as quantile regression and other rank-based approaches. Although randomization should obviate the need for any additional adjustment, we will explore whether adjustment for provider-level characteristics, such as demographics, panel size, or insurance mix, is necessary.

11 Source Documents and Access to Source Data/Documents

Source data is all information, original records of clinical findings, observations, or other activities in a study necessary for the reconstruction and evaluation of the study. Source data are contained in source documents. Examples of these original documents, and data records include: hospital records, clinical and office charts, laboratory notes, memoranda, subjects' diaries or evaluation checklists, pharmacy dispensing records, recorded data from automated instruments, copies or transcriptions certified after verification as being accurate and complete, microfiches, photographic negatives, microfilm or magnetic media, x-rays, subject files, and records kept at the pharmacy, at the laboratories, and at medicotechnical departments involved in the study.

The EPIC electronic health record is the primary data collection instrument for the study. Study-specific case report forms will not be used.

Access to study records will be limited to IRB-approved members of the study team. The investigator will permit study-related monitoring, audits, and inspections by the IRB/EC, the sponsor, government regulatory bodies, and University compliance and quality assurance groups of all study related documents (e.g., source documents, regulatory documents, data collection instruments, study data etc.). The investigator will ensure the capability for inspections of applicable study-related facilities (e.g., pharmacy, diagnostic laboratory, etc.).

12 Ethics/Protection of Human Subjects

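### Practice specialty is neither a stratification factor nor a term in the primary model; prespecifying it would be a near-free gain in precision

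*Combined protocol and SAP*

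**What the plan says.** The Protocol Summary describes the study sites as "approximately 70 outpatient practices in primary care, geriatrics, or endocrinology". The first inclusion criterion in section 5.1 reads "Patient at NYULH primary care or endocrinology practice". Section 4.1 describes a source pool "including 81 primary care and 21 endocrinology practices", plus 9 Family Health Center clinics, and adds that many sites are multispecialty. About 70 practices are to be chosen, but their mix by specialty is not given. Section 4.3 counts only the 81 primary care practices and does not mention endocrinology.

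The only stratification factor is size: "Randomization will be stratified by practice size", with the cut at 100 patients over 75 with diabetes. Allocation is 1:1, "with an even randomization ratio that will result in half of the sites randomized to the BE-EHR module activation".

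The primary analysis in section 10.3 is a Poisson mixed model of the provider-level compliance rate, "with treatment group as the primary fixed effect of interest and practice as a random effect to accommodate clustering of providers within practices". Beyond that, the plan will explore whether "adjustment for provider-level characteristics, such as demographics, panel size, or insurance mix, is necessary". Specialty is not named, and no rule says when an adjusted result would become the primary one.

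**The concern.** Section 4.4 builds the endpoint from two facts about a prescription encounter: whether the drug is a diabetes medication other than metformin, and whether the latest HbA1c lies in the patient's target range. Endocrinology and primary care practices may well differ on both. A practice's type is fixed before allocation, so it is an obvious candidate for a baseline covariate.

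If compliance does differ by specialty and the arms receive unequal numbers of endocrinology practices, part of the observed treatment difference reflects that imbalance. The unadjusted analysis also carries specialty variance in its standard error when a model term could remove it. Because adjustment is to be judged necessary or not during analysis, an imbalance would leave two candidate estimates and no prespecified choice between them.

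**Working it through.** **The plan's own figure.** Section 10.2 gives ICC 0.05, four providers per practice and 70 practices. The design effect is 1 + (4 − 1) × 0.05 = 1.15, and 280 / 1.15 = 243.5, which the plan gives as 244. Both reproduce. The stated power of about 87% for a 10-point difference cannot be reproduced from the stated inputs alone, because section 10.2 gives neither alpha nor the SD of the provider-level rate. With 122 effective providers per arm and two-sided 5% alpha, 87% requires an SD of about 0.253. This does not show that the 87% is wrong.

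**Assumptions made here**
- Provider-level SD 0.25, a round value close to 0.253.
- Two-sided alpha 5% and a normal approximation to the difference in practice means (the plan's model is Poisson).
- 35 practices per arm, ignoring size strata and blocks.
- Endocrinology share q = 21 / (81 + 21 + 9) = 0.189, about 13 of 70. This treats the 70 as a proportional draw from the pool.
- A compliance gap d between specialties, varied because the documents give none.

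**Variance components.** The total is 0.25² = 0.0625. The between-practice part is 0.05 × 0.0625 = 0.0031 and the within-practice part is 0.0594. The variance of a practice mean is 0.0031 + 0.0594 / 4 = 0.0180. The standard error of the difference is √(2 × 0.0180 / 35) = 0.0320, so power is Φ(0.10 / 0.0320 − 1.96), about 88%.

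**Chance shift.** The SD of the shift in the unadjusted estimate is d × √(q(1 − q) × 2 / 35). With q(1 − q) = 0.153 this is 0.094 × d, or about 0.9 points for d = 10 points. With 13 endocrinology practices, a split of 4 versus 9 or worse has probability about 22%.

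**Case A: the ICC of 0.05 already includes specialty.** Specialty variance is q(1 − q)d², and adjustment removes it from the between-practice part.
- d = 10 points: 0.153 × 0.01 = 0.0015 is removed. The practice-mean variance becomes 0.0164, the standard error 0.0306 and power about 90%.
- Ceiling: specialty cannot explain more than 0.0031, so d is at most √(0.0031 / 0.153), about 14 points. All between-practice variance is then removed, the standard error is 0.0291 and power about 93%. The shift SD is 0.094 × 14.3, about 1.3 points.

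**Case B: specialty variance comes on top of the ICC of 0.05.** The adjusted analysis keeps about 88%. The unadjusted analysis falls as follows.

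| Gap | Shift SD (points) | Unadjusted power | Implied total ICC |
|---|---|---|---|
| 10 points | 0.9 | 85% | 0.07 |
| 20 points | 1.9 | 77% | 0.13 |
| 30 points | 2.8 | 65% | 0.22 |

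The total ICC is (0.0031 + q(1 − q)d²) / (0.0625 + q(1 − q)d²).

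**Sensitivity to the mix (Case A, 10-point gap).** With 5 endocrinology practices of 70, the shift SD is 0.6 points and adjusted power about 89%. With all 21, they are 1.1 points and about 91%. The small loss from estimating the extra coefficient is ignored throughout.

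**The case against.** The strongest reply is that the size of the problem is undocumented and probably modest. No section reports compliance, prescribing or HbA1c by specialty. Even the direction of a gap is unknown, because the endpoint combines drug choice with HbA1c range. The number of endocrinology practices is also unknown. All of this stands, and specialty can be called plausibly prognostic but no more.

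A reader might infer that the missing term biases the result. The documents do not support that. Imbalance under randomisation is random error, and the practice random effect in section 10.3 carries between-practice specialty variance into the standard error, so inference stays valid.

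A reader might also take the 77% or 65% in Case B as the trial's likely power. Those figures require a total ICC of about 0.13 or 0.22, whereas section 10.2 calls 0.05 a conservative estimate of within-practice correlation. That correlation would ordinarily include similarity from shared specialty. Case B therefore mainly shows what a larger ICC would do.

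Finally, the list in section 10.3 is illustrative, so specialty is not excluded from exploration. That is fair, but exploration is not prespecification, and it leaves unsettled which result is primary. The multispecialty sites mentioned in section 4.1 mean that a single label per practice may not fit. This affects how the term is coded but does not remove the reason for it.

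**Conclusion.** The point holds as a missed gain in precision. Practices of different specialty are randomised together, stratified by size only, and analysed with no prespecified specialty term.

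Under the plan's own ICC, read as including specialty, a 10-point gap costs about 2 to 3 points of power. The most that can be lost is about 5 points, at a gap of about 14 points. The chance shift then has an SD of at most about 1.3 points, against a target effect of 10. Losses are larger only if specialty variance adds to the ICC of 0.05, which the documents do not suggest.

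These figures rest on an assumed SD of 0.25, a 19% endocrinology share, two-sided 5% alpha and an assumed gap. The validity of the primary analysis is not in question. The case for acting is that the change costs almost nothing and settles in advance how an imbalance would be handled.

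**What to change.** In section 10.3, prespecify specialty (endocrinology versus primary care/geriatrics) as a fixed effect in the primary model. Define it from information fixed before randomisation, and code it at provider level where a site is multispecialty. State that this adjusted estimate is the primary one.

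In section 4.3, state which practice types are randomised and, if known, how many of each, so that it agrees with the Protocol Summary and sections 4.1 and 5.1.

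The cost is a few lines of text and about one degree of freedom among 70 practices. The change can be made after randomisation, provided it is fixed before outcome data are examined by arm.

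Stratifying by specialty is optional, and possible only if randomisation has not yet been done. It would give four strata with size, and blocks of 4 and 6 in the small endocrinology strata would leave a few more incomplete blocks.
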